10.2 Baseline and Change from Baseline

Baseline is defined as the last non-missing assessment taken prior to the first dose of study vaccine.

Change from baseline is defined as:

$$\text{Observed result at nominal time point} - \text{observed result at baseline}$$

Change from baseline on the log scale is defined as $\log_{10} T1 - \log_{10} T0$.

10.3 Study Days and Visit Windows

Study Day 0 is defined as the date of the first vaccination, as recorded on the study vaccination administration eCRF. Other study days are defined relative to Study Day 0.

One month is defined as 30.4 days.

The scheduled study visits along with the predefined allowable visit windows are included in Table 3 below. No visit windowing will be performed for analysis purposes. Study results will be presented using the eCRF visits.

Table 3 Study Visits

Visit Name	Scheduled Vaccination	Study Day (Visit Window)
Screening		Day -42 to -1
Day 0/Baseline	Vaccination 1	Day 0
Day 1		Day 1 (+ 1d)
Day 7		Day 7 (+/- 1d)
Day 28	Vaccination 2	Day 28 (+ 2d)
Day 29		Day 29 (+ 1d)

Day 35		Day 35 (+/- 1d)
Month 3	MVA-HBV Boost ^a	Day 91 (+/- 7d)
Month 3 + Day 1 ^a		Day 92 (+ 1d)
Month 3 + Day 7 ^a		Day 98 (+/- 1d)
Month 6		Day 182 (+/- 7d)
Month 9		Day 273 (+/- 7d)

^a Only for participants who received the booster dose of MVA-HBV at Month 3 per the investigator's discretion.

10.4 Immunogenicity Endpoints

Immunogenicity samples (peripheral blood mononuclear cells; PBMCs) will be collected at planned time points.

The lower limit of quantification (LLoQ) for HBsAg is a value of 0.05 IU/mL, and any HBsAg value less than 0.05 IU/mL will be imputed by one-half of LLoQ, i.e., will be given a value of 0.025 IU/mL.

Any participants with a HBsAg < LLoQ will be classified as HBsAg-negative; participants with a HBsAg ≥ LLoQ will be classified as HBsAg-positive.

10.4.1 Geometric Mean (GM)

The geometric mean (GM) will be calculated as the anti-logarithm of the mean of the log-transformed result. The geometric standard deviation (GSD) will be calculated as the anti-logarithm transformation of the standard deviation of the log-transformed result. The 95% confidence interval will be calculated as the anti-logarithm transformation of the upper and lower limits for a two-sided confidence interval for the mean of the log-transformed results.

10.4.2 Seroconversion Rate

Seroconversion rates for HBeAg, HBeAb, HBsAg, and HBsAb will be defined as the following:

- **HBeAg seroconversion rate** is defined as the proportion of participants infected with Hepatitis B virus who are HBeAg positive at baseline and who are HBeAg negative at Month 9.
- **HBeAb seroconversion rate** is defined as the proportion of participants infected with Hepatitis B virus who are HBeAb negative at baseline and who are HBeAb positive at Month 9.
- **HBsAg seroconversion rate** is defined as the proportion of participants infected with Hepatitis B virus who are HBsAg positive at baseline and who have HBsAg < LLoQ (i.e. negative) at Month 9.
- **HBsAb seroconversion rate** is defined as the proportion of participants infected with Hepatitis B virus who are HBsAb negative at baseline and who are HBsAb positive at Month 9.

In addition, **sustained HBeAb positivity** is defined as the proportion of participants infected with Hepatitis B virus who are HBeAb positive at both baseline and Month 9.

10.4.3 ICS Response

Using the count data for each cytokine, cytokine responses (in percentages) are calculated based on the total number of respective T cell counts (CD4+ or CD8+) for each stimulation antigen separately (Core, Pol 1+2, Pol 3+4, Pre-S1/S2+S, DMSO).

For example:

CD4+ count = 83237 and CD4/CD107a+CD154+IFNg+IL2+TNFa+ count = 236, gives
 CD4/CD107a+CD154+IFNg+IL2+TNFa+ percent = 0.2835.

Overall cytokine response (%) for each T cell (CD4+, CD8+) by stimulation antigen is then calculated as:

- For CD4+: the sum of every CD4+ cytokine combination (%) where at least one of the following cytokines/functions is positive [+] (regardless of CD107a positivity). I.e., every CD4+ parameter except:
 - CD107a+CD154-IFNg-TNFa-IL-2-
 - CD107a-CD154-IFNg-TNFa-IL-2-
- For CD8+: the sum of every CD8+ cytokine combination (%) where at least one of the following cytokines/functions is positive (regardless of CD154 positivity). I.e., every CD8+ parameter except:
 - CD107a-CD154+IFNg-TNFa-IL-2-
 - CD107a-CD154-IFNg-TNFa-IL-2-

Missing values will not be imputed for this analysis.

Following the percent overall cytokine response calculation, for background (DMSO)-subtracted analyses only, the percent overall DMSO response is then subtracted from each percent overall cytokine response. To calculate the DMSO-stimulated response, no further calculations are required.

Background-subtracted responses that result in a negative value (<0) are set to zero.

Each cytokine pair per T cell (see Table 4) is also summed to form 15 cytokine combinations per stimulation antigen (required for the figures and listings). Note the all-negative response has not been included. For example:

$$\begin{aligned}
 &CD4/CD107a+CD154+IFNg+IL2+TNFa+ (\%) = 0.2835 \text{ and} \\
 &CD4/CD107a-CD154+IFNg+IL2+TNFa+ (\%) = 0.1 \\
 &\text{gives } IFNg+ / IL2+ / TNFa+ / CD154+ (\%) = 0.3835.
 \end{aligned}$$

Table 4 ICS Cytokine Response Combinations

T Cell	Cytokines (%)	Cytokine combination naming
CD4+	CD4/CD107a+CD154+IFNg+IL2+TNFa+	IFNg+ / IL2+ / TNFa+ / CD154+
	CD4/CD107a-CD154+IFNg+IL2+TNFa+	
	CD4/CD107a+CD154-IFNg+IL2+TNFa+	IFNg+ / IL2+ / TNFa+ / CD154-
	CD4/CD107a-CD154-IFNg+IL2+TNFa+	
	CD4/CD107a+CD154+IFNg+IL2-TNFa-	IFNg+ / IL2+ / TNFa- / CD154+
	CD4/CD107a-CD154+IFNg+IL2-TNFa-	IFNg+ / IL2+ / TNFa- / CD154-
	CD4/CD107a+CD154-IFNg+IL2-TNFa+	IFNg+ / IL2- / TNFa+ / CD154+
	CD4/CD107a-CD154-IFNg+IL2-TNFa+	IFNg+ / IL2- / TNFa+ / CD154-
CD4+	CD4/CD107a+CD154+IFNg+IL2-TNFa-	IFNg+ / IL2- / TNFa- / CD154+
	CD4/CD107a-CD154+IFNg+IL2-TNFa-	

T Cell	Cytokines (%)	Cytokine combination naming
	CD4/CD107a+CD154-IFNg+IL2-TNFa- CD4/CD107a-CD154-IFNg+IL2-TNFa-	IFNg+ / IL2- / TNFa- / CD154-
	CD4/CD107a+CD154+IFNg-IL2+TNFa+ CD4/CD107a-CD154+IFNg-IL2+TNFa+	IFNg- / IL2+ / TNFa+ / CD154+
	CD4/CD107a+CD154-IFNg-IL2+TNFa+ CD4/CD107a-CD154-IFNg-IL2+TNFa+	IFNg- / IL2+ / TNFa+ / CD154-
	CD4/CD107a+CD154+IFNg-IL2+TNFa- CD4/CD107a-CD154+IFNg-IL2+TNFa-	IFNg- / IL2+ / TNFa- / CD154+
	CD4/CD107a+CD154-IFNg-IL2+TNFa- CD4/CD107a-CD154-IFNg-IL2+TNFa-	IFNg- / IL2+ / TNFa- / CD154-
	CD4/CD107a+CD154+IFNg-IL2-TNFa+ CD4/CD107a-CD154+IFNg-IL2-TNFa+	IFNg- / IL2- / TNFa+ / CD154+
	CD4/CD107a+CD154-IFNg-IL2-TNFa+ CD4/CD107a-CD154-IFNg-IL2-TNFa+	IFNg- / IL2- / TNFa+ / CD154-
	CD4/CD107a+CD154+IFNg-IL2-TNFa- CD4/CD107a-CD154+IFNg-IL2-TNFa-	IFNg- / IL2- / TNFa- / CD154+
CD8+	CD8/CD107a+CD154+IFNg+IL2+TNFa+ CD8/CD107a+CD154-IFNg+IL2+TNFa+	IFNg+ / IL2+ / TNFa+ / CD107+
	CD8/CD107a-CD154+IFNg+IL2+TNFa+ CD8/CD107a-CD154-IFNg+IL2+TNFa+	IFNg+ / IL2+ / TNFa+ / CD107-
	CD8/CD107a+CD154+IFNg+IL2+TNFa- CD8/CD107a+CD154-IFNg+IL2+TNFa-	IFNg+ / IL2+ / TNFa- / CD107+
	CD8/CD107a-CD154+IFNg+IL2+TNFa- CD8/CD107a-CD154-IFNg+IL2+TNFa-	IFNg+ / IL2+ / TNFa- / CD107-
	CD8/CD107a+CD154+IFNg+IL2-TNFa+ CD8/CD107a+CD154-IFNg+IL2-TNFa+	IFNg+ / IL2- / TNFa+ / CD107+
	CD8/CD107a-CD154+IFNg+IL2-TNFa+ CD8/CD107a-CD154-IFNg+IL2-TNFa+	IFNg+ / IL2- / TNFa+ / CD107-
	CD8/CD107a+CD154+IFNg+IL2-TNFa- CD8/CD107a+CD154-IFNg+IL2-TNFa-	IFNg+ / IL2- / TNFa- / CD107+
	CD8/CD107a-CD154+IFNg+IL2-TNFa- CD8/CD107a-CD154-IFNg+IL2-TNFa-	IFNg+ / IL2- / TNFa- / CD107-
	CD8/CD107a+CD154+IFNg-IL2+TNFa+ CD8/CD107a+CD154-IFNg-IL2+TNFa+	IFNg- / IL2+ / TNFa+ / CD107+

T Cell	Cytokines (%)	Cytokine combination naming
	CD8/CD107a-CD154+IFNg-IL2+TNFa+ CD8/CD107a-CD154-IFNg-IL2+TNFa+	IFNg- / IL2+ / TNFa+ / CD107-
	CD8/CD107a+CD154+IFNg-IL2+TNFa- CD8/CD107a+CD154-IFNg-IL2+TNFa-	IFNg- / IL2+ / TNFa- / CD107+
	CD8/CD107a-CD154+IFNg-IL2+TNFa- CD8/CD107a-CD154-IFNg-IL2+TNFa-	IFNg- / IL2+ / TNFa- / CD107-
	CD8/CD107a+CD154+IFNg-IL2-TNFa+ CD8/CD107a+CD154-IFNg-IL2-TNFa+	IFNg- / IL2- / TNFa+ / CD107+
	CD8/CD107a-CD154+IFNg-IL2-TNFa+ CD8/CD107a-CD154-IFNg-IL2-TNFa+	IFNg- / IL2- / TNFa+ / CD107-
	CD8/CD107a+CD154+IFNg-IL2-TNFa- CD8/CD107a+CD154-IFNg-IL2-TNFa-	IFNg- / IL2- / TNFa- / CD107+

10.4.4 ELISpot Pooled Peptide Responders

The total (pooled over antigens) response for a participant at a given time point is calculated using the average (of the sample performed in triplicate) background-subtracted results (SFU/10⁶ PBMC) for each stimulation antigen:

- Total = Core + Pol1 + Pol2 + Pol3 + Pol4 + Pre-S + S
- Total (adjusted) = Core + Pol1 + Pol2 + Pol3 + Pre-S + S

For example using the average background-subtracted results (SFU/10⁶ PBMC) for each participant: Core=20, Pol1=26.67, Pol2=35, Pol3=56.67, Pol4=55, Pre-S=1.67, S=210, gives Total=405.

A participant is considered to have a response if the total (pooled over antigens) response is defined as greater than 51.6 SFU/10⁶ PBMCs or two times the background (DMSO) for that time point, whichever is higher.

Missing values will not be imputed for this analysis.

10.5 Adverse Events (AEs)

An adverse event is defined as any untoward medical occurrence in a participant administered a pharmaceutical product and does not necessarily have a causal relationship with this treatment.

All AEs entered on the eCRF will be coded according to the Medical Dictionary for Regulatory Activities (MedDRA) Version 23.0 or later.

10.5.1 AE Severity

The severity of AEs will be graded by the investigator as Grade 1 (Mild), Grade 2 (Moderate), Grade 3 (Severe), Grade 4 (Life-threatening), or Grade 5 (Fatal).

A change in severity of an adverse event will not be recorded as a new adverse event. Only the highest severity level that occurs during the entire period of the adverse event will be recorded on the eCRF with the onset and resolution dates encompassing the entire duration of the event.

Missing severity will not be imputed.

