## **8.2 Adverse Events**

### ***8.2.1 Definitions***

#### ***8.2.1.1 Adverse Event***

An adverse event is:

- Any untoward medical occurrence in a participant or clinical investigation subject administered a pharmaceutical product and which does not necessarily have to have a causal relationship with this treatment

- An adverse event can therefore be any unfavourable and unintended sign (including an abnormal laboratory finding), symptom or disease temporally associated with the use of study vaccine, whether or not considered related to the investigational product

An adverse event includes but is not limited to:

- Any clinically significant worsening of a pre-existing condition
- An adverse event occurring from overdose (i.e. a dosage higher than that prescribed by a healthcare professional for clinical reasons, or a dosage higher than that described in the Investigator's Brochure or on the marketed product label) of an investigational or marketed product, whether accidental or intentional
- An adverse event occurring from abuse (e.g. use for non-clinical reasons) of an investigational or marketed product
- An event related to a medical procedure or associated with the discontinuation of the previous use of an investigational or marketed product required by protocol (protocol related adverse event)
- Not all vital sign or laboratory abnormalities will be considered an adverse event. Usually these will be considered as an adverse event:
  - If Grade 3 (severe) or greater in severity
  - If judged to be clinically significant by the Investigator
  - If accompanied by clinical symptoms
  - If meeting the definition of a SAE
  - If resulting in dose modification, interruption or discontinuation of study vaccine
  - If requiring specific treatment

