**Table 3 Severity Grading of Adverse Events not listed in the Toxicity Table for Clinical and Laboratory Abnormalities**

Grade	Severity	
1	Mild	Asymptomatic or mild symptoms; clinical or diagnostic observations only; or intervention not indicated; no disruption of normal daily activity.
2	Moderate	Minimal, local, or non-invasive intervention indicated; discomfort sufficient to reduce or affect daily activity.
3	Severe	Severe or medically significant, but not immediately life-threatening; hospitalisation or prolongation of hospitalisation indicated; inability to work or perform normal daily activity.
4	Life-threatening	Represents an immediate threat to life.
5	Fatal	Death as a result of this adverse event

A change in severity of an adverse event will not be recorded as a new adverse event. Only the highest severity level that occurs during the entire period of the adverse event will be recorded on the eCRF with the onset and resolution dates encompassing the entire duration of the event.

Note: It is important to distinguish between serious and severe adverse events. Severity is a measure of intensity whereas seriousness is defined by the criteria in [Section 8.2.1.3](#).

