### *10.2.2.6 Safety Data*

Safety data will be summarised descriptively.

Treatment emergent events are defined as those occurring after study vaccine administration.

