10.6 Treatment-Emergent Events

Treatment-emergent events are defined as those occurring during or after the first study vaccine administration.

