10.9.1 Unsolicited AE Missing or Partial Dates

Unsolicited AEs will be considered treatment-emergent unless the partial start date indicates that the event began prior to first vaccination, i.e. if the month and/or year are before the month of first study vaccination.

For the purpose of determining if the unsolicited AEs falls within 28 days of each vaccination (vaccination date + 27 days), the following imputation of missing and partial start dates will be performed:

Missing day, month, and year

The day, month, and year of date of first vaccination will be assigned to the missing fields.

Missing day and month

If the year of the incomplete start date is the same as the year of the date of first vaccination, then the day and month of the date of first vaccination will be assigned to the missing fields.

If the year of the incomplete start date is before the year of the date of first vaccination, then December 31 will be assigned to the missing fields.

If the year of the incomplete start date is after the year of the date of first vaccination, then 01 January will be assigned to the missing fields.

Missing month only

The day will be treated as missing and both month and day will be replaced according to the above procedure.

Missing day only

If the month and year of the incomplete start date are the same as the month and year of the date of first vaccination, then the day of the date of first vaccination will be assigned to the missing day.

If either the year is before the year of the date of first vaccination or if both years are the same but the month is before the month of the date of first vaccination, then the last day of the month will be assigned to the missing day.

If either the year is after the year of the date of first vaccination or if both years are the same but the month is after the month of the date of first vaccination, then the first day of the month will be assigned to the missing day.

If the stop date is complete and the imputed start date is after the stop date, then the start date will be imputed using the stop date.

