12.7.1.1 Adverse Events

The number and percentage of participants reporting each adverse event, including the number of events, will be summarised by SOC and PT coded according to the MedDRA dictionary. Participants are only counted once within each SOC and PT. AEs will be sorted by decreasing frequency within each SOC and PT according to the overall treatment group.

In addition, summaries will be provided for the subset of AEs, SAEs, and Grade 3 or greater AEs that occurred within 28 days of first vaccination and second vaccination (vaccination day + 27 days) separately.

AESI will also be tabulated by PT for all events occurring during the study.

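### With one record per adverse event at its highest grade and first onset date, and no worsening clause, unsolicited events that worsen after a dose are left out of the TEAE tables or placed under the wrong dose.

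*SAP*

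**What the plan says.** **Recording.** SAP 10.5.1: "A change in severity of an adverse event will not be recorded as a new adverse event". Protocol 8.2.4.1 (below Table 3) carries the same rule, so it governs data collection as well as analysis: "Only the highest severity level that occurs during the entire period of the adverse event will be recorded on the eCRF", with onset and resolution dates that span the whole episode. An event that turns serious is re-flagged on its existing AE page and a SAE form is added (Protocol 8.2.6.1).

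**Treatment-emergent.** SAP 10.6: "Treatment-emergent events are defined as those occurring during or after the first study vaccine administration". Protocol 10.2.2.6: "Treatment emergent events are defined as those occurring after study vaccine administration". Neither mentions an increase in grade.

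**Timing.** SAP 10.9.1 works from the start date: "Unsolicited AEs will be considered treatment-emergent unless the partial start date indicates that the event began prior to first vaccination". To decide whether an event falls in a 28-day window, "the following imputation of missing and partial start dates will be performed". SAP 12.7.1.1 then summarises AEs, SAEs and Grade 3 or greater AEs "within 28 days of first vaccination and second vaccination (vaccination day + 27 days) separately".

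**Collection period.** Unsolicited AEs are collected from consent (Protocol 6 and 8.2.2), and screening runs from Day -42 to Day -1 (Protocol Table 2). SAP 12.7.2.1 plans a separate table for events that are not treatment-emergent.

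**Pre-existing conditions.** Protocol 8.2.1.1 counts as an AE "Any clinically significant worsening of a pre-existing condition", and Protocol 8.2.4.2 sends pre-existing conditions to baseline history.

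**The concern.** The primary endpoints (SAP 12.7.1) include the incidence of AEs, SAEs and Grade 3 or greater AEs in the four weeks after vaccination, and after dosing for the vaccines with nivolumab. SAP 12.7.1.1 turns this into separate tables for each dose. Those tables need to know when an event became severe. The record holds only when it began and the worst grade it ever reached, and nothing in either document captures the date of worsening or the grade held at each dose.

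Group 3 is where this matters most: its first dose is ChAdOx1-HBV alone and its second is MVA-HBV with nivolumab. A severe event that develops after the nivolumab dose from a mild event already present would be shown as severe after the nivolumab-free dose. The unsolicited-AE tables in the DMC and interim output list (SAP 16.0) are limited to treatment-emergent events, so a screening-period event that worsens after dosing would be missing from those as well. Vaccine-related SAEs and SUSARs still reach the DMC by separate notification (Protocol 8.1.5 and 8.2.5).

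**Working it through.** **Step 1: the plan's own safety figure.** SAP 8.1 and Protocol 10.1 state an 80% chance of detecting an event of 10% incidence with 16 participants. 1 − (1 − 0.10)^16 = 1 − 0.1853 = 0.8147, or 81.5%. The figure reproduces and is not in dispute.

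**Step 2: apply the written rules to example records.** Dose 1 is on Day 0 and dose 2 is taken on Day 28. The windows are dose day + 27 days, so Days 0–27 and Days 28–55. Each example is a Grade 1 event that rises to Grade 3. As written, TEAE status and window come from the onset day, and the grade is the maximum. In the last column, the Grade 3 window comes from the day of worsening.

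| Onset | Grade 3 on | As written | With dated worsening |
|---|---|---|---|
| Day -10 | Day 3 | not a TEAE; in neither window | TEAE; Grade 3 after dose 1 |
| Day -10 | Day 31 | not a TEAE; in neither window | TEAE; Grade 3 after dose 2 |
| Day 20 | Day 31 | TEAE; Grade 3 after dose 1 | TEAE; Grade 3 after dose 2 |
| Day 30 | Day 35 | TEAE; Grade 3 after dose 2 | same |

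Rows 1 and 2 are the first effect (left out of the TEAE tables). Row 3 is the second (wrong dose). Row 4 shows that an event that starts and worsens within one window is unaffected. Only two windows matter, because the SAP change history says that no participant had the Month 3 boost.

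**Step 3: effect of one case on a table cell.** Group sizes are 16 planned for Groups 2 and 3 (Protocol Table 1), and 10 and 9 for Groups 1 and 4 (SAP 8.1). 1/16 = 6.25%, 1/10 = 10.0%, 1/9 = 11.1%. One misplaced event therefore moves a cell by about 6 to 11 percentage points. In the second effect it moves two cells in opposite directions.

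**Step 4: illustration on the 80% statement.** Let f be the share of a dose's severe events that are worsenings of an event with an earlier onset. The documents give no value for f, so a range is shown. The chance that this dose's own table shows at least one event of 10% incidence is 1 − [1 − 0.10(1 − f)]^n.

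| f (assumed) | n = 16 | n = 9 |
|---|---|---|
| 0 | 81.5% | 61.3% |
| 0.10 | 77.9% | 57.2% |
| 0.25 | 71.3% | 50.4% |
| 0.50 | 56.0% | 37.0% |

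For example, with f = 0.25 and n = 16: 1 − 0.925^16 = 0.713.

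**The case against.** A reader might infer that severe events after nivolumab would disappear from the report, or appear only as first-dose ChAdOx1-HBV events, with a mild ALT rise or mild fatigue as the typical case. The documents do not support that.

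- **ALT.** Under Protocol 8.2.1.1, a Grade 1 laboratory change would not usually be an AE unless it is clinically significant, symptomatic, serious, treated or affects dosing. The AE would normally start at the escalation. ALT and AST are also summarised at each visit (SAP 12.7.1.2), and laboratory and vital-sign shifts use the worst post-baseline grade (SAP 12.7.2.3 and 12.7.2.4). None of this depends on AE onset.
- **Fatigue.** It is a solicited symptom, graded afresh for 7 days after each vaccination (SAP 10.5.5 and 12.7.2.2). Only a later escalation is exposed.
- **Events left out of the TEAE tables.** They remain in the non-TEAE table and the full listing (SAP 12.7.2.1). If they qualify as AESIs, they are also in the AESI table, which SAP 12.7.1.1 sets up without a 28-day limit. Protocol 10.2.2.6.1 requires narratives for SAEs and AESIs.
- **Events under the wrong dose.** They remain TEAEs at maximum grade in the correct group, and appear in the nivolumab-related tables if the investigator attributes them so (SAP 10.5.2 and 12.7.2.1).
- **Pre-existing conditions.** Worsening of a medical-history condition can be a new, post-dose AE under Protocol 8.2.1.1 and 8.2.4.2.

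All of this stands and narrows the point, but does not remove it. The pre-existing-condition provisions do not say what happens to an event already on the AE page before Day 0, where they collide with the no-new-record rule. They also do nothing for an event that starts after dose 1. Shift tables are not split by dose, and unsolicited clinical events outside the solicited list have no second route to the right dose. It could be argued that SAP 12.7.1.1 speaks of events that occurred in the window rather than started in it. But SAP 10.9.1 imputes start dates for exactly that purpose, and no other date is described.

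**Conclusion.** The point holds for unsolicited AEs. The written rules give a wrong classification in two situations: an event logged between consent and Day 0 that worsens after vaccination is not counted as a TEAE, and an event starting on Days 0–27 that reaches Grade 3 or greater after dose 2 is counted as Grade 3 or greater under dose 1 and not at all under dose 2. In the second situation the group, the grade and the TEAE status are right, and only the per-dose split is wrong. That split is how the SAP presents a primary safety endpoint, and in Group 3 it is also the split between nivolumab-free and nivolumab dosing.

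The number of such events cannot be worked out from the documents: no rate is given for events ongoing at a dose that later worsen. What can be said is that one case moves a cell by 6 to 11 percentage points in groups of 16 to 9. The detection figures above rest on an assumed f and show sensitivity only. Solicited AEs within 7 days of each vaccination, and the laboratory and vital-sign summaries, are not affected. The safety analysis is descriptive, so no test or error rate is involved.

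**What to change.** 1. In SAP 10.6, define a TEAE as an AE that starts, or increases in grade or becomes serious, on or after the first vaccination.
2. The wording alone is not enough, because the eCRF keeps only the highest grade. Query only AEs ongoing at Day 0 or at dose 2 for the date on which the grade rose or the event became serious. Assign the 28-day window in the Grade 3 or greater and serious tables by that date.
3. Where the date cannot be recovered, list the AEs ongoing at each dose and state the limitation in the report.
4. Reconcile Protocol 8.2.1.1 and 8.2.4.2 with the no-new-record rule for events that start between consent and Day 0.
5. If enrolment or follow-up continues, make the matching change to Protocol 8.2.4.1 in the next amendment. The SAP definition and the query do not need to wait for it.

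Cost: a SAP revision, a short round of site queries limited to events ongoing at a dose, some reprogramming of the per-dose tables, and slightly higher event counts.
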